- e After the study site is notified of end of study decision, an EOS Visit should be scheduled as soon as possible (but within 4 weeks at the latest).
- f For all participants still on treatment with study drug at the EOS Visit, the post-treatment (PT) telephone call (☎) has to be performed 30 days +5 days after the last intake of study drug.
- g For vital sign collection, please adhere to instructions in Section [8.2.2](#).
- h If BNP, NT-proBNP values (related to inclusion criteria) are not available in medical records, use values assessed by local laboratory.
- i Creatinine will be used to calculate eGFR using CKD-EPI ([Horio et al. 2010](#), [Levey et al. 2009](#))
- j If local laboratory data for potassium and eGFR are available within the last 24 hours, these may be used instead. This also applies when screening and baseline visits are not combined.
- k Study participants may have their local laboratory assessments taken up to 3 days prior to the study visit.
- l Female participants of childbearing potential must have a negative serum or urine pregnancy test at screening and baseline. Further serum or urine pregnancy tests should be performed in participants of childbearing potential as required by national/institutional regulations (e.g. at every visit). At any time during study participation, additional pregnancy testing should be performed upon suspicion of pregnancy.
- m All procedures at Visit 1 are to be performed prior to randomization.
- n One trough sample is to be collected at steady state before study intervention intake at Visit 3 (if not possible e.g. because study intervention was taken at home before the visit, the trough sample collection can be postponed to Visit 4 or 5); study intervention is to be administered at the study site at this visit.
- o Sample to be taken during the visit 1.5-10 hours after study intervention intake at home.
- p The procedures/assessments to be performed at the PD Visit are listed in the main SoA ([Figure 1-1](#)). After completing the PD Visit, all subsequent visits are to be performed according to the Premature Discontinuation SoA ([Figure 1-2](#)). Any visits performed prior to the PD Visit do not need to be repeated (e.g. if PD is at Visit 5, there is no need to repeat previous visits).
- q Questionnaires are to be completed by the participants before conducting any study procedure. See also Sections [8.1.1](#), [8.1.2](#) and [8.1.3](#) for details.
- r Only if applicable.

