#### 4.4 End of Study Definition

The end of study treatment period will be announced when the targeted number of primary endpoint events has occurred, unless the study is terminated early because of a recommendation of the DMC.

After notification of study end, an EOS Visit should be scheduled as soon as possible (but within 4 weeks at the latest) for all participants still participating in the study, to determine whether the participant had an event for inclusion in the primary or secondary endpoints.

The date on which the final participant performed the EOS visit is defined as the primary completion date (see schema in Section 1.2).

Participants still on treatment will stop study intervention treatment at the EOS Visit and must perform the PT Visit 30 +5 days after their last dose of study intervention.

Participants no longer taking study intervention must also be contacted as soon as possible after issue of the notification of end of study and be asked to attend the EOS Visit.

For participants who have objected to releasing further information after withdrawing from the study, an updated vital status should be obtained by the investigator from publicly available data sources, wherever allowed by local regulations. The collection of vital status must be obtained within the timelines provided by the sponsor at this time.

The end of the trial as a whole is defined as the date of the last PT Visit of the last participant in the trial globally.

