Time to total HF events will be analyzed with a joint frailty model (Rogers et al. 2016). This model gives a treatment effect on total HF events which is adjusted for a potential treatment effect on CV death. An effect on CV death might otherwise dilute the effect seen on the hospitalizations, i.e., an effective treatment will prevent CV deaths especially in the more severely ill participants, which then potentially realize many hospitalizations. The joint frailty model will be fitted using the method described in the paper by (Liu and Huang 2008) where the unknown baseline hazard for CV death and unknown baseline intensity for HF events are approximated by piecewise constant functions. A gamma frailty distribution will be assumed. As a sensitivity analysis a joint frailty model with constant hazard and intensity functions will be fitted as well. The flexible model can sometimes have convergence issues, should this occur, the estimate of HF events treatment effect of the model with the constant baseline functions will be considered to be the main estimate. The estimate from the joint frailty model for CV death will be considered supportive for the analysis of this component. The main analysis for the CV death component is described under the primary efficacy variable in section 9.4.1.1. As supportive analysis, a stratified Cox proportional hazard regression analysis of time to first HF event will also be performed.

The percentage of participants with improvement in NYHA class from Baseline to Month 12 will be analyzed with a logistic regression model including factors for treatment group and stratification levels. A patient is considered as having improved in NYHA class, if the NYHA class at Month 12 (Visit 6) is at least one category improved compared to the baseline visit. A composite strategy will be applied to those cases, where no measurement at Visit 6 is available, e.g. due to death or lost to follow-up. That means these patients are considered not improved in NYHA class. Odds ratio and two-sided 95% confidence intervals will be provided for the comparison of finerenone vs. placebo treatment group. In addition, change from baseline in NYHA class will be summarized descriptively using shift tables, presented by visit and any time post-baseline.

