4.4 Interim Analyses and Data Monitoring

One non-binding interim analysis for futility is planned when approximately 30% (~710) of the required total number of primary endpoint events have been observed. If the observed rate ratio (RR) on the primary endpoint is above 0.95, the trial is planned to be stopped for futility. This gives a probability of approximately 69% to stop under the null hypothesis (i.e. no treatment effect on the composite of HHFs and CV deaths) and leads to a loss in power of less than 1% under the alternative hypothesis of the treatment effect assumed for the sample size determination. No adjustment for this loss in power will be made.

The futility analysis given above is considered to be non-binding, the DMC will be asked to also consider important secondary efficacy endpoints as well as safety in their assessment.

In addition, one formal interim analysis for efficacy is planned when approximately 2/3 (~1580) of the required total number of primary endpoint events have been observed.

If the interim analysis shows clear and consistent benefit in the finerenone treatment group, the DMC may recommend early study termination. The Haybittle-Peto rule will be used to guide the decision regarding early stopping of the study for success: a reduction of 3 standard deviations (of the test statistic) in the analysis of the primary efficacy endpoint (two-sided p-value <0.0027) at the interim analysis. In addition, a nominal significant effect on the CV death component should be present (two-sided p-value<0.05) at the interim analysis. Note: The criterion for CV death would not be considered to prove formal statistical significance, as it does not keep the alpha level. It has been added so that the trial is only stopped at the interim if there is at least a certain amount of evidence of a beneficial treatment effect on CV death.

See Section 4.7 for a detailed description of the testing procedure, including an adjustment of the significance level for the interim analysis.

If the study is stopped early, the primary analysis reported in the CSR will consider all events up to the participants' respective EoS visits as would have been the case if the study had not stopped early. A sensitivity analysis will take all events up to the interim analysis datacut date into consideration. For this sensitivity analysis, censoring dates after the datacut date will be reset to the datacut date.

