4.7 Testing Procedure and Multiplicity Adjustment

If the interim analysis shows clear and consistent benefit in the finerenone treatment group (defined as two-sided p-value <0.0027 for the primary efficacy endpoint and two-sided p-value <0.05 for the CV death component at the formal interim analysis for efficacy) the DMC may recommend early stopping of the study for success (see Section 4.4 for full details).

If the study is stopped early for success: the final analysis for the primary endpoint will be performed at an overall two-sided significance level of 0.0027. Additionally, the secondary endpoints of:

- Total (first and recurrent) HF events
- Improvement in NYHA class from Baseline to Month 12
- Change from baseline to Month 6, 9 and 12 in TSS from KCCQ
- Time to first occurrence of composite renal endpoint

will be formally tested. The testing strategy of the secondary endpoints is as follows:

1. Total HF events will be tested at the 0.0027 two-sided significance level.
2. If the hypothesis of the secondary endpoint total HF events is rejected, the NYHA class and KCCQ endpoints will be tested using the Bonferroni-Holm procedure, i.e. if at least one of the hypotheses of the two endpoints NYHA class and KCCQ can be rejected at the two-sided (0.0027/2) significance level, the remaining of the two endpoints will be tested at the 0.0027 significance level.
3. If the hypotheses for all previous secondary endpoints are rejected, the composite renal endpoint will be tested at the 0.0027 significance level.

If the test for any endpoint produces a non-significant result, the testing of the remaining endpoints further down in the procedure will be performed in an explorative manner only.

Furthermore, the second component of the primary endpoint (CV deaths) will be tested at the 0.0027 two-sided significance level outside of the alpha-preserving procedure for the primary and other secondary efficacy endpoints (Total HF events, NYHA class, KCCQ, renal composite).

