The percentage of participants with improvement in NYHA class from Baseline to Month 12 will be analyzed with a logistic regression model including factors for treatment group and stratification levels. A patient is considered as having improved in NYHA class, if the NYHA class at Month 12 (Visit 6) is at least one category improved compared to the baseline visit. A composite strategy will be applied to those cases, where no measurement at Visit 6 is available due to stop of treatment prior to Visit 6. That means these patients are considered to have not improved in NYHA class. Participants who are still in the treatment period at Visit 6, but have NYHA assessment missing, will be imputed by taking the mean of the last available measurement prior to Visit 6 and the first measurement thereafter. Participants with no further value available after Visit 6 or whose only available information is from EoS visit will be imputed as non-responders. Participants with missing baseline value will be excluded from the analysis. Odds ratio and two-sided 95% confidence intervals will be provided for the comparison of finerenone vs. placebo treatment group. In addition, change from baseline in NYHA class will be summarized descriptively using shift tables, presented by visit and any time post-baseline. These tables will present the number of participants with the class at a certain visit by their respective baseline class.

The absolute change from baseline including measurements up to Month 12 of the KCCQ TSS will be analyzed by a repeated measures mixed model including the factors treatment group, baseline, visit, baseline-by-visit interaction, and factors for the stratification levels. For each treatment group a separate covariance pattern will be estimated based on an unstructured covariance to adjust for within participant variance.

In case the model does not converge, different covariance patterns will be used, in the following order, until convergence is met: separate unstructured covariance patterns, separate Toeplitz covariance patterns, separate Autoregressive(1) covariance patterns, and finally separate Compound Symmetry covariance patterns will be used.

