| Total HF events | Non-CV death is treated as a censoring event for a while-alive strategy. Additionally, the effect on total HF events is adjusted for a potential treatment effect on CV death |
| Improvement in NYHA class from Baseline to Month 12 | A composite strategy is applied when no measurement is available at Month 12 (due to death, or other reasons) |
| Change from baseline to Month 6, 9 and 12 in TSS from KCCQ | All observed values up to death for any cause are included, i.e. a while-alive strategy is used |
| Time to first occurrence of renal composite endpoint | All-cause death is treated as a censoring event for a while-alive strategy. If a participant had a decrease or decline in eGFR but died before a confirmatory eGFR measurement could be taken, then the event is counted for the analysis |
| Time to ACM | Not applicable |

This general approach is still considered valid despite the presence of the COVID-19 pandemic, considering the following factors:

- COVID-19 related study disruptions are expected to be equally likely to occur in either treatment group, therefore not creating bias for the treatment effect
- Information on most adjudicated endpoint events can still be collected even when physical visits cannot take place although incidences or reporting of some adjudicated events might change, e.g. as fewer participants might be hospitalized and have a higher risk of death

To quantify the impact of the COVID-19 pandemic, the following supplemental analyses will be performed:

- Primary endpoint (CV death and total HF events)
 - To address the hypothetical scenario in which participants did not experience any study disruption due to the COVID-19 pandemic, three separate analyses

will be conducted using the LWYY model described in Section 6.2.1.1 where participants are censored at

- a) Date of permanent discontinuation of study treatment due to COVID-19
- b) Date of first COVID-19 adverse event (SMQ narrow)
- c) Date of first direct or indirect COVID-19 study disruption

This analysis will be performed once including all primary efficacy events and once excluding those events adjudicated as related to COVID-19. For the latter analysis, the affected participants will be censored at the first occurrence of a COVID-19 related event

Additionally, plots and summaries of the mean cumulative function for the primary endpoint (Nelsen-Aalen estimate) will be presented by treatment group.

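### After an early stop for success, participants whose Month 12 visit was not yet due are scored as NYHA not improved, so the improvement percentages and risk difference are understated

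*SAP*

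**What the plan says.** - SAP 6.2.2.1 analyses NYHA improvement at Month 12 (Visit 6) by logistic regression and reports an odds ratio. Participants count as not improved where "no measurement at Visit 6 is available due to stop of treatment prior to Visit 6". Those still in the treatment period at Visit 6 with a missing value are imputed from neighbouring visits, but those with no later value, or "whose only available information is from EoS visit will be imputed as non-responders".
- Two other places describe the rule openly. SAP 6.5: "A composite strategy is applied when no measurement is available at Month 12 (due to death, or other reasons"). Protocol 9.4.1.2 applies it to cases "where no measurement at Visit 6 is available, e.g. due to death or lost to follow-up".
- Protocol 4.4: "Participants still on treatment will stop study intervention treatment at the EOS Visit". After notification of study end, "an EOS Visit should be scheduled as soon as possible (but within 4 weeks at the latest") (Protocol 1.3, note e).
- SAP 4.7 keeps NYHA in the formal hierarchy after an early stop, paired with KCCQ: "if at least one of the hypotheses of the two endpoints NYHA class and KCCQ can be rejected at the two-sided (0.0027/2) significance level", the other is tested at 0.0027. The renal endpoint follows only if every earlier secondary hypothesis is rejected.
- The early-stop text in SAP 4.4 says the primary analysis "will consider all events up to the participants' respective EoS visits". It deals with events and censoring and does not mention endpoints tied to a fixed visit.

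**The concern.** The efficacy interim can fall within a year of the last randomizations. A participant randomized eight months before study end has no Month 12 value because none was due. That participant stops drug at the EoS visit, so the first rule applies on its wording. If stop of treatment is taken to mean premature discontinuation only, the sentence on participants with no later value or only an EoS value gives the same result. Either way, study closure is recorded as failure to improve.

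NYHA is the only formally tested secondary endpoint handled this way. Total HF events and the renal endpoint are censored, and KCCQ enters a mixed model with observed values only. What is at stake is whether the reported percentages describe Month 12 improvement, plus some power at an already strict level.

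**Working it through.** **1. Reproduce the design.** Inputs from Protocol 9.2: 5500 participants, 1:1, 24-month recruitment (taken as uniform), 42 months in total; placebo rates per month of 0.0182 HF events and 0.005125 CV deaths; gamma frailty variance 5.0; non-CV death 0.0016 per month; HF rate ratio 0.75; CV death hazard ratio 0.80; 5% drug discontinuation per year with return to placebo risk. Simulation gives 2373 total events, 1308 first events, 533 CV deaths, 776 deaths and 89.7% power. The protocol states about 2375, 1310, 535, 775 and 90%. The model is reproduced.

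**2. Interim date.** 2/3 × 2375 ≈ 1583 events, reached on average at month 30.0. The last participant then has about 30 − 24 = 6 months of follow-up. The chance of meeting both early-stop criteria (primary p < 0.0027, CV death p < 0.05) under the design effect is about 29%.

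**3. Share not yet due for Visit 6.** Protocol 1.3 counts a month as 30 days, so Month 12 is 360 days, or 11.8 calendar months. With EoS visits at calendar month E, the share not yet due is (24 − (E − 11.8))/24:
- E = 31: (24 − 19.2)/24 = 20%
- E = 32: (24 − 20.2)/24 = 16%
- E = 33: (24 − 21.2)/24 = 12%

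The simulation also removes those who have died and gives 19%, 15% and 11%, about 600 to 1050 of 5500. The documents do not give the lag from data cut to EoS visits, so 1 to 3 months is an assumption.

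| Scenario | Interim (month) | Alive and short of Month 12, EoS 1 to 3 months after cut |
|---|---|---|
| N=5500, design rates | 30 | 19% to 11% |
| N=6000, rates ×0.9, 24-month recruitment | 30 | 20% to 12% |
| N=6000, rates ×0.9, 30-month recruitment | 33 | 25% to 18% |
| N=5500, rates ×0.8 | 34 | 3% to 0% |

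SAP 3 raised N to about 6000 because blinded event rates were lower than assumed. The size of the shortfall is not given, so the rate multipliers are assumptions.

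**4. Effect on the estimate.** If a share f in each arm is forced to not improved, a true proportion p is observed as (1 − f)p, and the risk difference is multiplied by (1 − f). The documents give no NYHA response rates; those below are assumed.
- f = 11%, 30% vs 26%: observed 0.89 × 30 = 26.7% and 0.89 × 26 = 23.1%. The difference falls from 4.0 to 3.6 points. The odds ratio goes from (0.30/0.70)/(0.26/0.74) = 1.220 to (0.267/0.733)/(0.2314/0.7686) = 1.210.
- f = 17%, placebo 20%, odds ratio 1.30 (finerenone 24.5%): observed 16.6% and 20.4%. The difference falls from 4.5 to 3.8 points, and the odds ratio from 1.30 to 1.28.

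**5. Power.** Two-proportion normal approximation, n = 2750 per arm: power = Φ{[(p1 − p0) − z√(2p̄(1 − p̄)/n)] / √[(p1(1 − p1) + p0(1 − p0))/n]}. Leaving participants out uses n(1 − f) with the true proportions; the SAP rule uses n with (1 − f)p. For f = 17%, placebo 20%, odds ratio 1.30:

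| | α = 0.0027 | α = 0.00135 |
|---|---|---|
| All reached Month 12 | 85.0% | 79.7% |
| Not-yet-due participants left out | 75.1% | 68.2% |
| SAP rule | 72.3% | 65.0% |

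The rule itself costs 75.1 − 72.3 = 2.8 points. The other 85.0 − 75.1 = 9.9 points come from Month 12 data that do not exist. Over f = 5-25% and placebo response 15-30%, the rule costs about 0.6-6 points at 0.0027 and 0.7-7 at 0.00135.

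**The case against.** **The branch may already be closed.** SAP 6.5 dates the trial's start to 14 September 2020, and SAP version 3.0 is dated 20 June 2024. Anyone still short of Month 12 on that date was randomized after about June 2023, some 33 months after the start, against a planned 24 months of recruitment. This stands as a caution. It is not proof, because the documents give neither the end of recruitment nor the interim outcome, and version 3.0 keeps the early-stop procedure.

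**Counting every missing value as failure is a legitimate conservative choice.** Also true. The wording in SAP 6.5 and Protocol 9.4.1.2 is open-ended, and no text says the rule was meant only for death or discontinuation. SAP 6.5 also tabulates reasons for non-improvement, including a category for other reasons, so the group would be partly visible. But a visit that was never due carries no information about the patient, and neither document states that the rule was meant to cover it.

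**The effect is small on the planned measure.** This stands; see steps 4 and 5 above.

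**Stronger readings a reader might infer.** One is that the rule biases the comparison or endangers error control. Study closure does not depend on arm, so it does neither. Another is that the rule blocks the renal test. That test also needs total HF events and KCCQ to be rejected, so the hierarchy sets that condition; the rule only lowers NYHA's chance slightly. A third is that KCCQ escapes untouched. It avoids imputed failures but still loses Month 12 data and, for some participants, Month 9 data.

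**Conclusion.** The point holds, within limits. After an early stop for success, the SAP as written scores participants not yet due for Visit 6 as not improved. Under the design assumptions this is about 11-19% of those randomized, with a scenario range from about 0-3% to about 25%. The improvement percentages and risk difference are understated by that fraction and would not describe improvement at Month 12. The consequence for the formal test is modest: a nearly unchanged odds ratio and about 3 points of power compared with leaving these participants out.

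The share rests on uniform recruitment, the Protocol 9.2 rates and a lag of 1 to 3 months to EoS visits. The power figures rest on assumed NYHA response rates. If the trial runs to its full event target, minimum follow-up is about 42 − 24 = 18 months and the issue does not arise.

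**What to change.** Add to SAP 6.2.2.1: if the study is stopped early for success, the NYHA analysis set is defined by randomization date alone. Everyone whose scheduled Visit 6 falls after study end is left out, whatever their outcome, including those who died or discontinued; their number is reported by arm. The text should name one calendar date as study end, for example the date of EoS notification. The existing composite rule stays for all other participants, and the analysis as now written is shown as a sensitivity analysis.

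The set should not be defined by who was still on drug at study end. That would drop late recruits who were doing well and keep those who died or stopped treatment, so the late cohort would contribute only failures. If discontinuation differed by arm, a dilution that is neutral between arms could become a small bias.

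The cost is a short SAP addition and a somewhat smaller NYHA analysis set in that branch. Nothing changes if the trial runs to its event target. If the interim has passed without a stop, or all participants are already past Month 12, a note saying so is enough.

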The other two components of the renal endpoint, i.e. initiation of dialysis or renal transplantation, will be adjudicated. To account for events of initiation of dialysis after the last eGFR is recorded at a clinic visit, such events will be included in the efficacy analysis of the composite renal endpoint if they occur in the period up to one day before the next planned clinic visit. Censoring will be applied at next protocol scheduled visit plus 1 month. For a death in this period, the date of death will be used as the censoring date. Randomized participants without an event of the composite renal endpoint at the time of analysis will be censored at the date of their last visit when complete information on all components of the composite renal endpoint is available, up to and including the EoS visit (should this visit satisfy this rule), or date of death using a time window next protocol scheduled visit plus 1 month as above if a subsequent clinic visit had been planned.

Additional supportive analyses will be considered and will be described in the SAP. The following subgroups will be considered in exploratory subgroup analyses for the primary and secondary efficacy variables. This will include descriptive statistics and a statistical test for interaction.

The randomization will be stratified by country/region and LVEF ( $<60\%$ ,  $\geq 60\%$ ). The most important subgroups besides stratification factors are given below (with further details and subgroups provided in the SAP):

- Baseline serum potassium ( $\leq 4.5$ ,  $> 4.5 \text{ mmol/L}$ )
- eGFR category at baseline (eGFR 25 to  $<45$ , 45 to  $<60$ ,  $\geq 60 \text{ mL/min/1.73 m}^2$ )
- Atrial fibrillation at baseline ECG (present, absent)
- Diabetes mellitus at baseline (present, absent)
- HHF (very recent [ $\leq 7$  days before randomization], recent [ $>7$  days –  $\leq 3$  months],  $>3$  months -  $\leq 6$  months,  $>6$  months -  $\leq 9$  months,  $>9$  months -  $\leq 12$  months, no index).

It is anticipated that in these proposed subgroups for analysis, differences in treatment effects may be observed according to the screening or baseline characteristics defined, due in part to the differences in the risk of clinical events expected in the different subgroups.

Furthermore, subgroup analysis usually required will be performed, including the following subgroups:

- Race
- Sex
- Age group.

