Only central laboratory measurements before initiation of dialysis or renal transplantation will be considered for the definition of the individual eGFR-based components of the renal endpoint. At the up-titration, restart and safety check visits, only a local laboratory measurement is obtained. These values will be checked for a potential eGFR event and, in case of decline, the investigators will be advised to retest eGFR centrally in an unscheduled visit; determination of an eGFR event will then be based on this value. If an initial decrease in eGFR occurs on the EoS visit, there will be another confirmatory measurement taken at least 4 weeks later to confirm the initial decrease. The individual components “Sustained decrease of eGFR $\geq 50\%$ from baseline over at least 4 weeks” as well as “Sustained eGFR decline $<15\text{ml/min}/1.73\text{m}^2$ ” will be programmatically derived. Only in the event that the eGFR decrease was confirmed by at least one additional eGFR measurement taken at least 4 weeks later, it will be considered as a sustained decrease and counted for the renal endpoint. The confirmatory additional eGFR measurements will typically be taken during an unscheduled visit. The date used for the analysis will be the date of the initial sample exceeding the threshold. If there was no confirmatory assessment, events will only be counted for the renal endpoint when the patient died after the initial decrease or the patient went on renal replacement therapy such as dialysis or transplantation prior to their scheduled confirmatory assessment. If there is an intermediate measurement that does not confirm the initial decrease, the event will not be counted for the renal endpoint.

eGFR events will be counted from the day of randomization until the EoS visit (or EoS notification + 28 days if EoS visit is missing). Participants will be censored at the earliest of the date of their last visit when a central eGFR measurement is available or EoS visit date (or EoS notification + 28 days if EoS visit is missing). If no post-baseline eGFR measurement is available, participants will be censored at day 1 (randomization date).

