The other two components of the renal composite endpoint, i.e. initiation of dialysis or renal transplantation, will be adjudicated. To account for events of initiation of dialysis or renal transplantation after the last eGFR is recorded at a clinic visit, such events will be included in the efficacy analysis of the composite renal endpoint if they occur in the period up to the next planned clinic visit (+ 1 month) or EoS visit date (or EoS notification + 28 days if EoS visit is missing) or death date or last contact date. If no post-baseline eGFR measurement is available, the next planned visit is the date of Visit 2 (Month 1). Censoring will be applied at the last eGFR date (or day 1 if last eGFR date is missing) or at the earliest of EoS visit date (or EoS notification + 28 days if EoS visit is missing) or death date or last contact date, if these occur earlier than the next eGFR date + 1 month.

Randomized participants without an event of the composite renal endpoint at the time of analysis will be censored at the latest censoring date of their individual components.

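### Renal composite: a participant followed beyond the dialysis/transplant window is censored back at the last eGFR, so for that subgroup the window counts as time at risk only if an event occurs

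*SAP*

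**What the plan says.** SAP 6.2.2.1 handles the two kinds of renal component separately.

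- **eGFR components.** Event-free participants are censored "at the earliest of the date of their last visit when a central eGFR measurement is available", or at EoS if that is earlier.
- **Dialysis and transplantation, counting.** Events after the last eGFR count "if they occur in the period up to the next planned clinic visit (+ 1 month) or EoS visit date", followed by substitutes for a missing EoS visit and by death and last contact. The list is joined by 'or', without saying earliest or latest.
- **Dialysis and transplantation, censoring.** The sentence has two limbs. The first reads "Censoring will be applied at the last eGFR date (or day 1 if last eGFR date is missing"). The second takes the earliest of EoS visit (or its substitute) "or death date or last contact date, if these occur earlier than the next eGFR date + 1 month".
- **Composite.** Participants without an event "will be censored at the latest censoring date of their individual components".

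Protocol 9.4.1.2 differs. It counts initiation of dialysis "if they occur in the period up to one day before the next planned clinic visit", and then says "Censoring will be applied at next protocol scheduled visit plus 1 month", or the date of death for a death in that period. Its next sentence also names the last visit with complete information on all components as the censoring date. The SAP change log for version 3.0 records that renal censoring was updated, without a reason.

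**The concern.** Counting and censoring dates should agree: if an event on a given day would be counted, an event-free participant observed on that day should be at risk on it. The first limb of the SAP rule breaks this. A participant followed past the window contributes an event if dialysis falls inside it, but no time from it if dialysis does not occur. Censoring then depends on the outcome, and observed event-free follow-up is discarded.

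The composite is formally tested, last in the hierarchy (SAP 4.7), by stratified log-rank test and Cox model. A rule that removes risk time selectively could shift the hazard ratio if gaps in central eGFR sampling are more common in one arm.

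**Working it through.** **Reproduction.** The documents give no event count, rate, effect size or power for this endpoint, so there is no planned figure to reproduce. The rule was traced on example participants, then its likely effect was simulated.

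**Step 1: window length.** Window end = next planned on-site visit + 1 month, using the Protocol 1.3 schedule. The counting list is read as the earliest of its dates, and 'next eGFR date' as the next planned clinic visit.

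| Last central eGFR | Next planned visit | Window end | Length (months) |
|---|---|---|---|
| None post-baseline | M1 | M2 | 2 |
| M1 | M3 | M4 | 3 |
| M3, M6, M9 | M6, M9, M12 | M7, M10, M13 | 4 |
| M12, M16, M20 | M16, M20, M24 | M17, M21, M25 | 5 |

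The 5 months agree with the window in the on-treatment analysis of SAP 6.2.2.3.

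**Step 2: trace the rule.** Last central eGFR M20, next planned visit M24, window end M25. The protocol column applies its visit + 1 month rule.

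| Participant | SAP | Protocol |
|---|---|---|
| Contact to M36, no dialysis | Censored M20 | Censored M25 |
| Contact to M36, dialysis M23 | Event M23 | Event M23 |
| Contact to M36, dialysis M24.5 | Event M24.5 | Not counted, censored M25 |
| EoS or death at M22 | Censored M22 | Censored M22 |
| Last contact M23, no event | Censored M23 | Censored M23 |
| Last contact M26, no event | Censored M20 | Censored M25 |

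Rows 4 and 5 are matched. Rows 1 to 3 and row 6 are not. Under the SAP, last contact at M23 gives 23 months at risk and last contact at M26 gives 20. The composite's latest-date rule does not help, because the eGFR components are also censored at M20.

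**Step 3: size.** From the documents: N = 6000, 1:1, follow-up of 18 to 42 months (taken as uniform). Assumed, not in the documents: eGFR-event rate 0.8 per 100 patient-years; dialysis/transplant rate 0.2, 0.5 or 1.0 per 100 patient-years; 10% or 20% of participants stop central eGFR between Months 12 and 24 but stay in contact; true hazard ratio 1. There were 400 replicates with an unstratified log-rank at two-sided 5%. Each simulated trial was analysed under three rules: SAP, matched window, and events and time both stopped at the last eGFR. Only differences between rules are informative: with about 182 events the simulation error of a mean log hazard ratio is about (2/√182)/√400 = 0.007.

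- Events after the last eGFR: 0.42 of 142.5 (0.3%) to 4.17 of 247.5 (1.7%).
- Risk time added by matching: 14,271 − 14,082 = 189 patient-years (1.3%) to 14,031 − 13,646 = 385 (2.8%).
- Equal gaps: SAP and matched hazard ratios differ by at most 0.0002. Rejection under the SAP rule was 3.75% to 5.75%, with a simulation standard error of √(0.05 × 0.95/400) = 1.1%.
- Gaps of 10% versus 20%, with the 20% arm in the numerator:

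| Dialysis/transplant rate | SAP | Matched | Stop at last eGFR | SAP − matched | SAP − stop |
|---|---|---|---|---|---|
| 0.2 | 1.0172 | 1.0025 | 1.0163 | 0.0147 | 0.0009 |
| 0.5 | 0.9953 | 0.9809 | 0.9902 | 0.0144 | 0.0051 |
| 1.0 | 1.0069 | 0.9923 | 0.9995 | 0.0146 | 0.0074 |

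**The case against.** The case for leaving the rule alone has four parts.

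*The affected group is narrow.* This stands. The second limb matches time whenever EoS, death or last contact falls inside the window. Participants off study drug still have central eGFR on the Premature Discontinuation schedule, EoS is expected on site, and any later central sample closes the gap. A reader might infer that everyone followed by telephone is affected. The documents do not support that: telephone contacts alternate with on-site visits for all participants after Month 12. The subgroup is nevertheless foreseeable, because Protocol 7.1 lets telephone consultations replace visits off treatment, and SAP 6.5 and 6.6 expect most adjudicated events to be captured when visits cannot take place.

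*The protocol is no cleaner.* This also stands. A reader might infer that the protocol was symmetric and the SAP broke it. In fact the protocol counts to the day before the next visit but censors a month after that visit, and it also names the last complete visit. It is inconsistent in a different way.

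*The numerical effect is small.* It is, and a loss of 1.3% to 2.8% of patient-years is not itself a bias in a hazard ratio.

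*Matching has a price.* The added months contain no eGFR measurements, so eGFR events cannot be seen in them. With unequal gaps, the matched hazard ratio sits 0.007 to 0.014 below the rule that stops everything at the last eGFR, further away than the SAP rule does. Most of the 0.015 therefore reflects this unobservable time, and should not be read as pure error in the SAP rule. Stopping events and time together is also coherent, but it discards adjudicated events the SAP means to keep. The second limb already accepts the same price for participants whose follow-up ends inside the window.

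**Conclusion.** The rule is wrong as written for one identifiable subgroup: participants whose central eGFR sampling stops, who remain in contact at or beyond the next planned visit plus 1 month, and who have no later sample. For them, time at risk depends on the outcome, and longer follow-up can yield less of it. That ordering has no evident rationale and looks like a drafting slip.

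The expected consequence is small. With balanced gaps the hazard ratio and type I error are essentially unaffected. With gaps of 10% versus 20%, the SAP-rule hazard ratio is about 0.015 above the matched-window value and 0.001 to 0.007 above that from stopping at the last eGFR. These sizes rest on assumed event rates and gap proportions. The documents give neither, and do not show that gaps differ by arm. A reader might infer that the renal result is materially biased; nothing here supports that. The case for correction is that a formally tested endpoint needs one coherent, programmable risk window.

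**What to change.** In SAP 6.2.2.1, define one window end for dialysis and transplantation: the earliest of (i) the next planned clinic visit after the last central eGFR plus 1 month, (ii) the EoS visit, or EoS notification plus 28 days if that visit is missing, (iii) death, and (iv) last contact. Count these events up to that date and censor event-free participants at the same date. The existing latest-component rule then carries the date to the composite. Stating 'earliest' and using a single term for the next visit also removes the ambiguity in the counting list.

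Reconcile this with Protocol 9.4.1.2, whose counting limit and two censoring statements do not agree with each other or with the SAP.

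Add a sensitivity analysis that stops both events and time at the last central eGFR, because eGFR events cannot be observed in the added months. Reporting by arm how many participants have such a gap would show whether the choice matters.

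The cost is one rewritten SAP sentence, one changed derivation, one extra model run and a documented reconciliation with the protocol. No new data are needed.
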